5.5 Management of Compliance and Deviations from Protocol

The Principal Investigator and sub investigator of this clinical study shall become fully aware of the protocol and perform the study so that the protocol is not violated. To follow the administration and test schedule of the investigational product in this study, the sub investigator shall take proper measures so that the subject makes an outpatient visit on the relevant date (for example, written notice of the next visit time or phone monitoring).

In case of major protocol violation, the subject shall be dropped out from analysis (Excluded from PP analysis) in principle and the following apply to this.

1. In case of no acquiring the informed consent
2. In case of violation of the inclusion/exclusion criteria
3. If the subject takes contraindicated drugs during study period
4. In case of an error in randomization

For minor protocol violations which are not deemed to influence the analysis of study results, the degree of violation or delay shall be exactly mentioned, and when a final report is written, whether or not the study has been influenced by the investigator, sponsor, monitor, and statistician shall be comprehensively evaluated in PP analysis.

CHAPTER 6. INVESTIGATIONAL PRODUCT

6.1 Overview of the Investigational Product

6.1.1 Study drug

1. Brand name : Epodion® 2000 IU
2. Manufacturer : PT. Daewoong Infion
3. Appearance : Colorless yellowish pre-filled syringe
4. Storage : 2-8 °C

6.1.2 Control drug

Control drug that is used as a comparator is Eprex® (Janssen).

6.2 Dosage, Administration, and Administration Period

The drug dose should be individualized, during titration period Eprex® doses should be closely titrated to achieve target Hb range 10-12 g/dl. During maintenance period, the administration dose of Eprex® and Epodion® is equal to the previous dose in titration period. Dose is allowed to be increased or decreased during maintenance period at an appropriate level to maintain Hb level 10-12 g/dl according to condition of subjects. Route of administration for this study is Intravenous injection (IV). Investigational product will be administered when subject enrolled until the end of the study.

6.3 Management of Investigational Products

6.3.1 Shipment and storage conditions of study drug

The study drug shall be kept in a safe place with limited access. The study drug shall be refrigerated at 2°C - 8°C. Temperature shall be closely observed throughout the clinical study and recorded in the specified form. If the drug is frozen, or if refrigeration has stopped, the drug shall not be given. In such case, the investigator or sub-investigator shall make inquiries to the monitor to take actions.

The clinical trial pharmacist shall store and manage study drugs to ensure guaranteed drug quality until given to patients.

6.3.2 Inventory of study drug

The clinical trial pharmacist responsible for drug procurement and control shall record must record the amount of drug used for research and reporting to sponsors for reimbursement purposes. If shortage of drugs is expected during the study period, clinical trial pharmacist shall be immediately reported to the clinical study monitor to avoid delays in drug supply. The sponsor's monitor shall make sure that there is consistency between the drug control record of the institution and record of the case report form.

6.4 Concomitant Medication and Treatment

6.4.1 Concomitant medication

The following drugs may be concomitantly administered during the study period.

- a. Any drug the subject has been on medication prior to participating in the clinical trial, the drug which is considered not to affect the study result analysis shall be permitted during the study period by the clinician's judgement.
- b. Any drug to be used temporarily for the purpose of treating other diseases or adverse events incurred during the study period shall be concomitantly administered through discussion with the investigator or physician.

All the information (commercial name, indication, daily dose, administration period etc.) of concomitant medications (including medication to treat other diseases or adverse events) shall be recorded in the CRF in detail.

6.4.2 Contraindications

Epodion is contraindicated in patients with the following conditions:

- a. Hypersensitivity to other drugs or Erythropoietin products
- b. Patients who develop pure red cell aplasia (PRCA) following treatment with any erythropoietin
- c. Uncontrolled hypertension
- d. Hypersensitivity to derivative products from mammalian cells or albumin
- e. Patients experience events that result in severe damage to coronary, peripheral, carotid or cerebral vessels.
- f. Patients scheduled to follow any surgery who for any reason cannot receive adequate antithrombotic prophylaxis or treatment

CHAPTER 7. STATISTICAL ANALYSIS PLAN

7.1 Definition of analysis group

7.1.1 Safety Set

The Safety Set will consist of all enrolled subjects who received at least 1 dose of the investigational product. In the case of dosing administration error, analyses on the Safety Set will be conducted according to actual treatment received.

7.1.2 Full Analysis Set (FAS)

The Full Analysis Set will be consisting of all randomized subjects who treated for at least 4 weeks of the investigational product, and for whom at least 1 Hb level for the evaluation period will be available. In the case of dosing administration error, analyses on the FAS will be conducted according to randomized treatment.

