5.4 Temporary Discontinuation

If the following situation occurs, the investigator shall delay investigational product administration until the situation will be settled. Then, investigational product administration shall be delayed to the extent of investigational product administration schedule indicated.

The following condition when investigational product should be delayed are detailed below:

- Increase blood pressure systole ≥ 180 mmHg and/or diastole ≥ 120 mmHg.
- Hb level exceed 13 g/dL, investigational product should be reinitiated at approximately 25% lower than the previous dose after haemoglobin levels fall to 12 g/dl (7.45 mmol/l) or below.
- Any reason based on the assessment of the principal investigator.

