7.1.3 Per-Protocol Set (PPS)

The Per-Protocol Set will be defined as all subjects who completed the study without any major protocol deviations. The subjects who committed a major protocol deviation will be finally determined in the blind meeting before database lock.

In the study, the efficacy assessment will have the PPS as the primary analysis set, and the FAS will be additionally analyzed and the results of the two analysis sets will be compared.

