7.4 Efficacy Analysis

Efficacy analysis will be performed using the Full Analysis Set and Per-Protocol Set.

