7.4.2 Secondary Endpoint

(1) Change in weekly dosage per kg body weight from baseline to the evaluation period.

Descriptive statistics will be provided treatment group. The difference between treatment groups will be analyzed by ANCOVA model with treatment as factor, and baseline Hb level and baseline weekly dosage per kg body weight value as covariates.

(2) Instability rate of Hb level during maintenance and evaluation period

The number of subjects with Hb level <8 g/dl or Hb level >13 g/dl during maintenance and evaluation period will be provided by treatment groups along with rates and the two-sided 95% confidence intervals. Also, the difference in the rates between the treatment groups and two-sided 95% confidence interval will be provided.

(3) Hb and Hematocrit level during maintenance and evaluation period

Descriptive statistics will be provided treatment groups for Hb and Hematocrit levels at baseline and at each bi-week during maintenance and evaluation period. The time course figure of Hb levels will be presented using mean and standard deviation throughout maintenance and evaluation period.

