7.6 Handling of dropout or missing values

Analysis for efficacy variables will be performed for subjects who have at least 1 Hb level for the evaluation period. For by visit analysis (ANCOVA, Hb and Hematocrit level), missing data will be imputed by LOCF (last observation carried forward) method. For calculating the instability rate, only observed data will be used. For safety analysis, no imputation will be made for missing data.

CHAPTER 8. ADVERSE EVENTS

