### **1.3. Per-Protocol Set (PPS)**

The Per-Protocol Set will be defined as all subjects who completed the study without any major protocol deviations. The subjects who committed a major protocol deviation will be finally determined in the blind meeting before database lock.

In the study, the efficacy assessment will have the PPS as the primary analysis set, and the FAS will be additionally analyzed and the results of the two analysis sets will be compared.

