### **3.4. Handling of dropout or missing values**

Analysis for efficacy variables will be performed for subjects who have at least 1 Hb level for the evaluation period. For by visit analysis (ANCOVA, Hb and Hematocrit level), missing data will be imputed by LOCF (last observation carried forward) method. For calculating the instability rate, only observed data will be used. For safety analysis, no imputation will be made for missing data.

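### A subject who withdraws during maintenance is in neither efficacy set, so the FAS-PPS comparison cannot show the effect of that dropout and the instability rate omits Hb events that were observed

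*Protocol*

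**What the plan says.** - **FAS** (Protocol 7.1.2, same text in SAP 1.2): randomised subjects "treated for at least 4 weeks of the investigational product, and for whom at least 1 Hb level for the evaluation period" is available.
- **PPS** (Protocol 7.1.3, SAP 1.3): "all subjects who completed the study without any major protocol deviations". The PPS is primary for efficacy; "the FAS will be additionally analyzed and the results of the two analysis sets will be compared".
- **Sets used for efficacy** (Protocol 7.4, SAP 3): "Efficacy analysis will be performed using the Full Analysis Set and Per-Protocol Set". No third set is named.
- **Missing data** (Protocol 7.6, SAP 3.4): "Analysis for efficacy variables will be performed for subjects who have at least 1 Hb level for the evaluation period". LOCF for the by-visit analyses comes after that sentence. Then: "For calculating the instability rate, only observed data will be used".
- **Instability rate** (Protocol 7.4.2, SAP 3.2): "The number of subjects with Hb level <8 g/dl or Hb level >13 g/dl during maintenance and evaluation period", by arm, with 95% confidence intervals.
- **Timing** (Protocol 4.4, 4.4.4, 4.4.5): maintenance is weeks 9-32 or 13-36, with blood drawn every two weeks. Evaluation is weeks 33-36 or 37-40. For a withdrawn subject the study ends on the exit date.
- **Leaving** (Protocol 5.3, 5.4): dropouts are asked to attend a final visit. Four consecutive weeks without product is a dropout criterion. When Hb exceeds 13 g/dL, "the investigator shall delay investigational product administration until the situation will be settled".

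**The concern.** In an equivalence trial a second analysis set is useful when it keeps subjects whom the per-protocol set loses. Here both sets select on the same post-randomisation fact: reaching the evaluation period. If withdrawal during maintenance is related to Hb and differs between arms, the PPS and the FAS lose the same people. Agreement between the two sets then says nothing about that loss.

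The instability rate has a more direct problem, which needs no assumption about bias. Its definition covers maintenance. A qualifying Hb recorded in week 20 is inside the period and is observed, yet it is not counted if the subject leaves in week 24.

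**Working it through.** **1. Trace of one subject.** Take a subject who is randomised, has several biweekly Hb values in maintenance, and withdraws before the evaluation period.

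| Rule | Requirement | Result |
|---|---|---|
| Protocol 7.1.2 / SAP 1.2 (FAS) | an evaluation-period Hb | out |
| Protocol 7.1.3 / SAP 1.3 (PPS) | study completion | out |
| Protocol 7.4 / SAP 3 | efficacy in FAS and PPS only | in no efficacy analysis |
| Protocol 7.6 / SAP 3.4, first sentence | an evaluation-period Hb for any efficacy variable | LOCF not reached |
| Protocol 7.4.2 / SAP 3.2 (instability) | a secondary efficacy endpoint, so the same condition holds | maintenance Hb <8 or >13 not counted |
| Protocol 7.1.1 / SAP 1.1 (Safety Set) | one dose | kept, for safety summaries only |

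The FAS-PPS contrast still picks up major deviations, and subjects who leave after a first evaluation-period Hb.

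**2. How many subjects.** Protocol 3.2 (rationale for the number of subjects) inflates 90 for 10% dropout. This reproduces: 90 / (1 - 0.10) = 100. Up to 10 of 100 subjects could be outside both sets if all dropout fell in maintenance. The 10% is a planning assumption, not a bound, and part of it may fall elsewhere. (Exact two one-sided tests at the stated inputs give 80.5% power at 90, not 90%. That is a separate matter and is not used here.)

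**3. Effect on the Hb comparison (illustration).**
- From the plan: SD 0.8, margin ±0.5, 90% CI, 10% dropout.
- Assumed: true all-randomised difference -0.5 g/dL, 5 dropouts per arm (45 analysed), unadjusted comparison.

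With dropout share q, -0.5 = (1 - q) × C + q × D. Here C and D are the between-arm differences among completers and among dropouts, so C = (-0.5 - 0.1 × D) / 0.9. The standard error is 0.8 × √(2/45) = 0.169 and t(0.95, 88 df) = 1.662. The half-width is therefore 0.280, and the observed difference must lie within ±0.220. Exact power integrates over the sampling distribution of the SD.

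| D (g/dL) | C (g/dL) | Equivalence declared |
|---|---|---|
| 0 | -0.556 | 2.4% |
| -0.5 | -0.500 | 5.0% |
| -1.0 | -0.444 | 9.4% |
| -1.5 | -0.389 | 16.1% |

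The effect can go either way. Every D in the table is assumed.

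**4. Effect on the instability rate (illustration).** Simple arithmetic: an arm of 50, 5 leaving in maintenance, and an assumed 10% rate in the other 45 (4.5 expected events). The plan reports 10%. Counting everyone gives:
- (4.5 + 1.5)/50 = 12% if 30% of the leavers had an event;
- (4.5 + 2.5)/50 = 14% if 50% had;
- (4.5 + 5)/50 = 19% if all had;
- 4.5/50 = 9% if none had, so the full rate can also be lower.

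A simulation that follows the Hb route in Protocol 5.4 and 5.3 assumed SD 0.8, autoregressive correlation 0.85 between biweekly visits, pre-randomisation mean 11.0, and post-randomisation mean 11.0 or 11.5. The 10-12 g/dL entry range of Protocol 5.2 was applied, with no dose adjustment and no fall in Hb after a hold. The true rate is about 3.5% / 14.5%. If 10% of readings above 13 end in withdrawal, the plan reports about 3.0% / 12.3%, a loss of 0.5 / 2.2 percentage points.

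**The case against.** **The PPS is primary and would not change.** True. What is affected is a supportive analysis and a secondary rate that has no decision rule. But the plan itself sets the two sets side by side, and a reader will take agreement as reassurance about dropout.

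**The subjects are not lost: the Safety Set keeps them.** True. Adverse events leading to discontinuation and clinically significant laboratory results are summarised by arm. Those tables give neither the instability rate nor the effect on the Hb comparison.

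**The final visit might supply the missing Hb.** Only if it falls in weeks 33-36 or 37-40. No rule assigns it to the evaluation period, and the study ends at exit.

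**The observed-data sentence might exempt the instability rate.** It says which values to use, not which subjects. The sentence that selects subjects covers all efficacy variables and makes no exception.

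**Stronger readings that the documents do not support.** A reader might infer that high Hb commonly leads to exclusion, through the delay in Protocol 5.4 and then the four-week criterion in 5.3. The text allows that path. It does not say whether a protocol-directed delay counts towards the four weeks, or how often Hb stays high that long. A reader might also infer that low Hb drives dropout, but 5.3 lists no such criterion. Both arms are also dosed to hold Hb at 10-12 g/dL, which limits excursions. These points stand, so no frequency or direction can be claimed.

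**Conclusion.** The structural point holds on the text alone. A maintenance-period withdrawal without an evaluation-period Hb is outside every efficacy analysis. The FAS-PPS comparison is blind to it, and the instability rate leaves out events observed in the period it is defined on.

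The size is unknown. For Hb, bias needs a between-arm difference among dropouts that departs from that among completers. With a true difference at the margin and 10% dropout, the range shown runs from 2.4% to 16.1% around the nominal 5.0%. For instability, the gap is small unless withdrawal after such readings is common.

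It would go too far to conclude that the primary equivalence result is biased, that the FAS-PPS comparison has no use, or that the reported instability rate must be too low. The documents support none of these. The clinical rules in Protocol 5.3 and 5.4 are not in question. This should be fixed before database lock; it does not undermine the primary analysis.

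**What to change.** 1. **Instability rate.** Compute it from observed Hb in all randomised subjects with at least one dose of randomised product and at least one post-randomisation Hb. Report follow-up time and number of Hb measurements by arm beside it, because an early leaver without an event would otherwise count as stable.
2. **FAS.** Define it as that same set, analysed as randomised (Protocol 7.1.2, SAP 1.2). Delete the sentence in Protocol 7.6 and SAP 3.4 that requires an evaluation-period Hb.
3. **Hb analysis.** Keep the PPS ANCOVA primary, with its decision rule unchanged. In the FAS, replace LOCF with a pre-specified likelihood-based repeated-measures model on the biweekly Hb: treatment, visit, treatment-by-visit and baseline Hb. Give the 90% CI for the treatment contrast averaged over the evaluation visits, and state the missing-at-random assumption. The dose-change covariate has no value for a subject without evaluation-period dose data, so this model omits it. Show a PPS analysis without that covariate beside it, so that a change of covariate is not mistaken for a change of population.
4. **Other items.** Restrict the dose-change endpoint to subjects with evaluation-period dose data. Use observed data without LOCF for the by-visit Hb and hematocrit summaries. Report withdrawals by arm, time and reason.

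**Cost.** Wording changes and a little more programming; the Hb values are already scheduled every two weeks. The supportive analysis relies on missing at random, which the data cannot confirm. The FAS-PPS contrast remains descriptive in a trial of this size.

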7.1.3 Per-Protocol Set (PPS)

The Per-Protocol Set will be defined as all subjects who completed the study without any major protocol deviations. The subjects who committed a major protocol deviation will be finally determined in the blind meeting before database lock.

In the study, the efficacy assessment will have the PPS as the primary analysis set, and the FAS will be additionally analyzed and the results of the two analysis sets will be compared.

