3.1 Study Design

This study is an open label, randomized, active drug-comparative, parallel-designed, multi-center study in hemodialysis patients with anemia.

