7.4.1 Primary Endpoint

Change in Hb levels from baseline to the evaluation period

Descriptive statistics will be provided by treatment group. The difference between treatment groups will be determined by ANCOVA (analysis of covariance) model with treatment as factor, and baseline Hb level and the change in weekly dosage per kg body weight from baseline to the evaluation period of Epodion® or Eprex® as covariates.

Therapeutic equivalence of Epodion® to the comparator Eprex® will be demonstrated if the two-sided 90% confidence interval of the difference of mean changes in Hb levels between treatment groups lay within the interval of ± 0.5 g/dL.

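### Nothing says what follows if the per-protocol and full analysis sets disagree on equivalence, so a per-protocol pass alone meets the written criterion

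*Protocol*

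**What the plan says.** Protocol 7.1.3, repeated in SAP 1.3, states that "the efficacy assessment will have the PPS as the primary analysis set, and the FAS will be additionally analyzed". The only use given for the second analysis is that "the results of the two analysis sets will be compared". Protocol 7.4 and SAP 3 add that "Efficacy analysis will be performed using the Full Analysis Set and Per-Protocol Set", without ranking the sets.

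The decision rule is in Protocol 7.4.1 and SAP 3.1: "Therapeutic equivalence of Epodion® to the comparator Eprex® will be demonstrated if the two-sided 90% confidence interval" for the difference in mean Hb change lies within ±0.5 g/dL. No analysis set is named there.

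The sets are defined as follows:
- **PPS:** "all subjects who completed the study without any major protocol deviations". Protocol 5.5 lists the major violations: no informed consent, an eligibility violation, a contraindicated drug during the study, and a randomisation error. The final decision is taken at a blind meeting before database lock.
- **FAS:** "all randomized subjects who treated for at least 4 weeks of the investigational product". There is a second condition, on the outcome: the set is limited to those "for whom at least 1 Hb level for the evaluation period will be available".

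On blinding, Protocol 3.1 says: "This study is an open label, randomized, active drug-comparative, parallel-designed, multi-center study in hemodialysis patients with anemia".

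**The concern.** Read together, these sections make the per-protocol interval the deciding one and attach no consequence to the full-analysis interval. If the first lies inside ±0.5 g/dL and the second does not, the written criterion is met, and the weight given to the disagreement would be settled after the results are known.

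Neither set is safe alone for an equivalence claim. Deviations kept in the FAS can dilute a real difference, and exclusions from the PPS can remove one. Taking a contraindicated drug and failing to complete both happen after randomisation, when site staff know the arm. Protocol 5.3 also lets the investigator end participation on his or her own assessment. If the subjects lost this way tend to be those with the poorest Hb response in one arm, the PPS difference is pulled towards zero. The stake is a false claim of equivalence at more than the nominal 5%.

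**Working it through.** **Inputs.** From Protocol 3.2: margin ±0.5 g/dL, SD 0.8 g/dL, assumed difference 0, 90 evaluable subjects (45 per arm), 10% dropout. From 7.4.1: two-sided 90% interval. Assumed, because the documents give no figures: 45 per arm in the FAS, the PPS nested within it, and the exclusion patterns below. An unadjusted t-interval stands in for the planned ANCOVA.

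**1. The plan's own figure.** The plan gives 90 evaluable subjects for 90% power, and about 100 enrolled. The dropout step is right: 90/0.9 = 100. The power is not reproduced. Exact power for two one-sided 5% tests is 80.5% at 90 subjects, and 90% power needs 114. That is a separate sample-size point; here it only sets the base from which the cost is counted.

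**2. What a pass requires at 45 per arm.**
- Standard error = 0.8 × √(2/45) = 0.169.
- Half-width = 1.662 × 0.169 = 0.280.
- The interval lies inside ±0.5 when the observed difference is within ±(0.5 − 0.280) = ±0.220.
- At a true difference of −0.5, P(observed > −0.220) = P(Z > 0.280/0.169) = P(Z > 1.66), about 5%, as intended.

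**3. Effect of outcome-related exclusions in one arm.** Removing k subjects whose mean lies a SDs below their arm's mean raises that arm's mean by k × a × 0.8/(45 − k). The approximate pass probability is then P(Z > (0.280 − shift)/0.169). The values of a are expected order-statistic means for 45 normal values. The simulation (100,000 runs per case) also allows for the smaller SD left after trimming.

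| Excluded from the Epodion arm | a | Shift (g/dL) | Approximate | Simulated, PPS only | Simulated, both sets |
|---|---|---|---|---|---|
| 1 lowest | 2.21 | 0.040 | 8% | 8% | 5% |
| 2 lowest | 2.01 | 0.075 | 11% | 12% | 5% |
| 4 lowest | 1.75 | 0.137 | 20% | 22% | 5% |
| 2 at random from the lowest 15 | 1.07 | 0.040 | 8% | 8% | 5% |
| 4 at random from the lowest 15 | 1.07 | 0.084 | 12% | 12% | 5% |

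**4. Exclusions unrelated to outcome.** With 2 or 4 removed at random from each arm and the true difference still at the margin, the PPS passes in about 5% of trials and both sets pass in about 4%. Without informative exclusion there is no inflation.

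**5. Cost when the products are truly equal.** At a true difference of 0, with 4 random exclusions per arm, power is about 75% on the PPS alone and 73% if both sets must pass. With 2 per arm it is 78% and 76%. The PPS passes while the FAS fails in only 2% to 3% of these trials.

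**6. What the FAS can protect against.** A subject who leaves before the evaluation period (weeks 33-36 or 37-40) has no Hb value there and is in neither set. If the four lowest subjects in step 3 left that early, both sets would lose the same people and the both-sets rule would also pass about 22% of the time. The 5% column applies only to subjects who are in the FAS but not in the PPS.

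**The case against.** A reader might infer that the plan says a failed FAS cannot stop the claim. No text says so. Both sets are to be analysed, the results must be compared, and the decision rule names neither set. The defect is silence about disagreement, not a stated instruction to ignore the FAS. That stands.

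Making the PPS primary is a defensible choice for an equivalence question and is not criticised here. A prespecified procedure for explaining discordance would be another acceptable way to fill the gap.

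The plan also has safeguards. Major violations are listed in advance, only some arise after randomisation, and Hb is a laboratory value. The final decision is taken at a blind meeting before database lock. This is some protection, but the documents do not say how those at the meeting are kept from treatment assignment in an open-label trial. Protocol 5.5 also excludes major violators only in principle, and leaves the influence of minor violations to be judged when the final report is written.

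The error rates come from a true difference exactly at the margin and outcome-selected exclusions in one arm. Nothing in the documents predicts such patterns. This objection stands in full: the figures are stress tests, not forecasts.

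A reader might also infer that requiring both sets holds the error at 5% in general. It does not, because the FAS itself omits early withdrawals.

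**Conclusion.** The point holds as a missing decision rule. As written, a PPS interval within ±0.5 g/dL satisfies the criterion whatever the FAS shows, because neither the protocol nor the SAP names the deciding set in the rule or says what follows from disagreement.

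Under the stated stress-test assumptions, PPS-only false equivalence is about 8% to 22%, against about 5% when both sets must pass. If exclusions are unrelated to outcome, it stays at about 5%. The risk is therefore conditional on informative exclusion between the FAS and the PPS. The documents neither show that this will happen nor rule it out. The rule should be changed before database lock, mainly because both analyses are already planned and the change is small.

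**What to change.** In Protocol 7.4.1 and SAP 3.1, state that therapeutic equivalence is concluded only if the 90% confidence interval lies within ±0.5 g/dL in both the PPS and the FAS, and that equivalence is not demonstrated if the two disagree. Reword Protocol 7.1.3 and SAP 1.3 so that the comparison of the two sets refers to this rule. It would also help to say how those attending the blind meeting are kept from treatment assignment.

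**Cost:** a sentence or two of text, no new data, and about 2 to 3 points of power. The base is already about 80% at 90 evaluable subjects rather than the planned 90%, so joint power would be about 73% to 76% in the cases in step 5. Restoring about 90% would take about 114 evaluable subjects (114/0.9, so about 127 enrolled). That belongs with the sample-size question and is not caused by this change.

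**Limit:** the rule covers only exclusions between the FAS and the PPS. Testing the effect of earlier withdrawals would need a further analysis of all randomised subjects.
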